### **10.2 Data Management Plan**

The Data Management Center (DMC) of the Division of Biostatistics and Epidemiology (DBE) will provide full data management support for this study. In collaboration with the study team and the CDC, case report forms will be developed. The DMC will develop the data capture system using a web-based data collection system, REDCap, as the primary source of data entry and storage. REDCap is a software toolset and workflow methodology for electronic collection and management of research and clinical trial data developed by Vanderbilt University, with collaboration from a consortium of institutional partners including the University of Cincinnati Academic Health Center. REDCap provides HIPAA-compliant and 21 CFR Part 11-ready audit trails for tracking page views, data manipulation and export procedures. A copy of coded data with the unique study ID number but without personal identifiers will be sent to CDC upon request; patient identifiers will be kept at CCHMC; no identifying information will be included on any data sent to the CDC.

REDCap is hosted on a network specially designed to support the rigorous security and compliance requirements of basic, clinical and translational research projects. Administered by the Division of Biomedical Informatics (BMI), this network features multiple firewalls as well as a central facility for managing hosted systems and users. The result is another layer of access control and audit capability on top of what REDCap already provides.

### **10.3 Data Analysis Plan**

Primary objectives - Statistical Analysis.

#### **a) Descriptive statistics:**

Descriptive statistics will be calculated for all demographic, anthropometric, reactogenicity, serum, image and fecal variables. For continuous variables, five-number (mean, SD, minimum, median, maximum) summaries will be produced. For class (categorical) variables, frequencies and percentages will be reported. Descriptive statistics will be calculated for the entire study population, as well as for each vaccine group at each time point. Investigators will be advised by study statisticians about potential outliers, or data entry issues, based on these summary statistics. To determine whether continuous serum, image and fecal outcomes meet the assumption of a Gaussian (normal) distribution, the Shapiro-Wilk test will be used. Where a significant departure from normality exists, an appropriate transformation of the data will be employed prior to inferential analyses. If transformations are not successful, non-parametric analyses will be used.

**b) Inferential statistics**

The primary analysis for this study is the comparison of anatomical outcome as measured by MRI between (RV1, RV5 with and without other vaccines: 4 groups) and within (pre and post) study groups. The primary anatomical outcome will be the terminal ileum thickness measured in mm. The change in this outcome before and after vaccination will be compared for each study group (within group test) using a paired t-test, while the between group difference at pre, post and on the difference between pre and post (change score) will be initially analyzed using general linear model (GLM) where the ileum thickness (at pre, post and change score) is modeled as a function of group (4-groups). Depending on the result of the F-test from the GLM analysis, this will be followed by pairwise comparison between groups (6-comparisons). This will be examined using a two sample t-test. If the difference between groups with and without other vaccines for a given vaccine (RV1 or RV5) is not significant we might combine the categories and conduct a comparison test for the outcome between the two vaccine types. If the primary outcome is not normal before or after transformation we will use the non-parametric Kruskal-Wallis test to compare the groups. Although the primary between group comparisons is based on the pre-post change score, we are conducting additional analysis based on the pre and post data to get more insight about the distribution of the primary outcome variable.

We will also examine the distribution of socio-demographic and other potential covariates among the groups using a GLM analysis. If some covariates are differentially distributed among the groups, those covariates will be controlled for in the primary analysis described above. Potential modifiers such as breast milk or secretor status will be examined by modeling the primary outcome as a function of group, potential modifier and the interaction between group and modifier. In this case the parameter of interest is the coefficient of the interaction term, however it is possible that the interaction test might not be sensitive due to sample size. Regardless we will examine and report the observed change between groups for each potential modifier as a subgroup. For example we will report difference between groups in the primary outcome for secretors and non-secretors separately.

To assess how vaccine shedding is related with the primary outcome by looking at the correlation between the imaging outcome and the fecal shedding for each group (using sample obtained close in time with the imaging). This will be examined using Pearson or Spearman correlation coefficients based on the normality of the data. The resulting correlation coefficient from each group can be compared with each other (pairwise) using Fisher's transformation and compare the resulting z-scores. If the correlation are not different we may then combine the groups and run the correlation across group to get an insight on the relationship between shedding and imaging parameter.

For all the other imaging parameters (cecum thickness, wave pattern and amplitude) similar analysis described for the primary outcome (ileum thickness) will be conducted. For Lymph node presence a logistic regression instead of GLM, and for the lymph node number, and wave frequency a Poisson regression will be used.

For the cytokines outcome (IL2, IL6, IL7, IL8, IL15, TNF) similar analysis described for the primary imaging outcome including examination of modifying variables and potential subsequent stratified analysis will be conducted.

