#### 3.3 Primary and Exploratory Objectives

Primary Objectives:

- 1) to examine the effects of RV1 and RV5 with or without other routine immunizations on gastrointestinal anatomy
- 2) to assess the feasibility of conducting a larger scale study

Exploratory Objectives:

- 1) to examine the effects of RV1 and RV5 with or without other routine immunizations on gastrointestinal motility
- 2) to examine the effects of RV1 and RV5 with or without other routine immunizations on blood and stool cytokines and inflammatory responses, including clinical reactogenicity events
- 3) to assess patterns and level of vaccine virus shedding after RV1 and RV5
- 4) to provide preliminary data assessing associations with the pattern of rotavirus vaccine strain (RV1 and RV5) shedding in the stool and blood, stool cytokine responses, and the anatomy and/or functional motility of the small intestine; and examine other factors such as maternal antibody, breast milk antibody, and human blood group antigens to see if these factors modify these responses
- 5) to compare MRI and ultrasound imaging

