Recruitment and enrollment will occur prior to the first study visit. There will be three scheduled study visits after recruitment/enrollment. . Infants will be randomized to either RV1, RV1 plus other immunizations, RV5 alone, or RV5 plus other immunizations. Visit 1 (day 0) will include blood, saliva, stool and breast milk collection . The MRI and ultrasound will be performed prior to vaccination. Children will receive the immunizations to which they are randomized. Imaging personnel and parents will be blinded to rotavirus vaccine type; they will be informed about other vaccines administered. A second MRI and ultrasound will be performed at Visit 2 (day 5) and blood and stool samples collected. Parents will be unblinded at the completion of Visit 3 (day 14). Arrangements will be made to get remaining doses of same rotavirus vaccine. Daily stool samples will be collected at home during the 15 day study period (on vaccination day 0 and for next 14 days). A memory aid will be completed to collect reactogenicity data on days 0 and for the next 14 days. Remaining stools and reactogenicity data from parents will be collected at Visit 3. **See Appendix 1 for detailed description of visits and timeline.**

We will assess blood and stool cytokine responses and intestinal anatomy and motility after rotavirus vaccination by comparing pre-vaccination with post-vaccination responses in the study infants. Cytokines and intestinal anatomy and motility will be assessed at baseline (Visit 1, the day of vaccine receipt) and 5 days after vaccination (Visit 2). For both blood and stool, the following cytokines will be tested: IL-2, IL-6, IL-7, IL-8, IL-15, INF- $\gamma$  and TNF- $\alpha$ . Additional biomarkers may be studied. The 5 day period post-vaccination was chosen because this time period corresponds with the peak period for intestinal replication of rotavirus vaccine virus for both vaccines.

In order to protect the health of infants, we will provide procedures to facilitate and assure that infants enrolled in the study will receive the routinely recommended vaccines for 2 month old infants which are DTaP, Hib, PCV13, HBV and IPV that will also allow them to get their 4 month vaccines on schedule.

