#### **4.4 Randomization and Study Withdrawal**

##### **Randomization Procedures**

The randomization code will be prepared by statisticians in the Epidemiology and Biostatistics Core at CCHMC. The randomization code will link to the vaccine assignment. The subject will be assigned a randomization code. Randomization will take place prior to the vaccine administration, but after the parent/legal guardian has given permission/informed consent, signed the IRB-approved consent form and met all of the inclusion and none of the exclusion criteria. Infants will be randomized 1:1:1:1 to one of four groups: 1) RV1 alone, 2) RV5 alone, 3) RV1 with routine immunizations (DTaP, Hib, PCV13, HBV and IPV or 4) RV5 with routine immunizations.

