## 6 STUDY PROCEDURES

### 6.1 Rotavirus Vaccine Randomization and Administration

Infants will be randomized to receive 1) RV1 alone, 2) RV5 alone, 3) RV1 with routine immunizations (DTaP, Hib, PCV13, HBV and IPV or 4) RV5 with routine immunizations prior to Visit 1. They will receive the vaccination(s) after the MRI/Ultrasound is completed at Visit 1.

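### Primary objective 1 is partly answered by within-arm pre-post tests although every arm receives a rotavirus vaccine, so a within-arm change should be labelled uncontrolled and not attributed to vaccination

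*Combined protocol and SAP*

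**What the plan says.** Section 3.3 gives the first primary objective as "to examine the effects of RV1 and RV5 with or without other routine immunizations on gastrointestinal anatomy". In section 10.3, under Inferential statistics, "The primary anatomical outcome will be the terminal ileum thickness measured in mm". The primary analysis there compares the four groups with one another "and within (pre and post) study groups". The within-group part is a paired t-test in each arm: "The change in this outcome before and after vaccination will be compared for each study group (within group test) using a paired t-test". The between-group part is a general linear model with an F-test and possible pairwise tests. The pre and post values are also modelled, for insight; the change score is what counts: "Although the primary between group comparisons is based on the pre-post change score".

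Section 4.1 describes the route to the answer in the same pre-post terms: "We will assess blood and stool cytokine responses and intestinal anatomy and motility after rotavirus vaccination by comparing pre-vaccination with post-vaccination responses".

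On allocation, section 4.4 says "Infants will be randomized 1:1:1:1 to one of four groups: 1) RV1 alone, 2) RV5 alone, 3) RV1 with routine immunizations", and section 6.1 completes the list with "4) RV5 with routine immunizations prior to Visit 1". No arm is untreated, given placebo, or given routine vaccines only. Nothing in the documents limits how a within-arm change may be read or names the missing comparator as a limitation.

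**The concern.** A paired t-test asks whether the mean change is zero, not why it differs from zero. The protocol itself creates several reasons for a change between day 0 and day 5 that are not the rotavirus vaccine:

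- a second fast and a second oral contrast feed (6.6);
- residual differences in bowel distension between the two scans;
- reader expectation: section 9.13 states blinding to time point only for the second anatomic reader, on a random subset, and the blinding of radiologists in 10.1 is to arm, which does not protect a pre-post comparison;
- in two arms, routine vaccines given the same day, which the background section on other routine immunizations links to raised inflammatory markers.

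A non-vaccine shift could therefore be read as an anatomical effect of vaccines linked to intussusception, or a shift in the opposite direction could mask a real effect. The Power paragraph of 10.3 says effect sizes will be reported to help design later studies, so a within-arm effect size could carry the shift forward. Section 10.3 also applies similar analyses to other imaging parameters and to the cytokines.

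**Working it through.** The plan has no power, SD, effect size or alpha to reproduce; the Power paragraph says the sample size was predetermined. The check has two parts.

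**What each analysis identifies.** Write the expected mean change in an arm as D + V + R. D is the non-vaccine drift common to all arms, V is the effect of the rotavirus vaccine given (V1 or V5), and R is the effect of same-day routine vaccines (zero in the two arms without them). R is taken as the same with either rotavirus vaccine, for simplicity.

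- Paired test in RV1 alone: tests D + V1 = 0.
- Paired test in RV5 with routine vaccines: tests D + V5 + R = 0.
- RV1 alone minus RV5 alone: V1 − V5. D cancels.
- RV1 with minus RV1 without routine vaccines: R. D cancels, and so does V1.
- If V1 = V5 and R = 0, all between-arm contrasts are zero however large V1 is.

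So the paired test cannot separate V from D, and the randomised contrasts cannot see a V common to all arms. No contrast in the design isolates rotavirus vaccine against none.

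**How often drift alone gives significance.** Inputs from the documents:

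- Up to 150 infants, 1:1:1:1 (4.1, 4.4): 150 / 4 = 37.5, taken as 37 per arm. This is an expected ceiling, since randomisation is simple (10.1).
- The goal that at least 70% complete both MRIs (Appendix 2): 0.70 × 37 = 25.9, about 26 pairs per arm.

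Assumed, not in the documents: two-sided alpha 0.05, zero vaccine effect, normal change scores, drift d of 0 to 0.4 SD of the change, and independent arms.

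Formula: the test statistic is noncentral t with n − 1 degrees of freedom and noncentrality d√n. The rejection probability is p = P(|t| > t(0.975, n − 1)), with critical values 2.028 for n = 37 and 2.060 for n = 26. For example, at n = 37 and d = 0.3 the noncentrality is 0.3 × √37 = 1.825, giving p = 0.427. The chance of at least one of four is 1 − (1 − p)^4; here 1 − 0.573^4 = 0.892.

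| Drift (SD of change) | One arm, 37 pairs | At least one of 4, 37 pairs | One arm, 26 pairs | At least one of 4, 26 pairs |
|---|---|---|---|---|
| 0 | 0.050 | 0.185 | 0.050 | 0.185 |
| 0.1 | 0.091 | 0.317 | 0.078 | 0.277 |
| 0.2 | 0.220 | 0.629 | 0.165 | 0.515 |
| 0.3 | 0.427 | 0.892 | 0.313 | 0.777 |
| 0.4 | 0.658 | 0.986 | 0.500 | 0.938 |

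The no-drift row matters. Four unadjusted tests already give 1 − 0.95^4 = 0.185, a separate multiplicity matter; only the excess over that row is due to drift.

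In 20,000 simulated trials at each of 0, 0.3 and 0.5 SD of common drift, for 37 and for 26 pairs per arm, the four-group F-test on change scores rejected in 4.7% to 5.1%. The randomised comparison is unaffected.

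**The case against.** The strongest reply is that the plan makes no causal claim from the paired tests. It sets no success rule for them, and its wording about change before and after vaccination is temporal. This is a pilot whose other primary objective is feasibility, and no power was claimed. That stands: a reader might infer that the plan already declares a significant within-arm change to be a vaccine effect, and the text does not say so. What remains is that an objective worded as effects, joined to within-arm tests inside the primary analysis, invites that reading, and nothing in the text guards against it.

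Second, several nuisance sources are partly controlled. Fasting and scan order are planned alike at both visits, one scanner type and a weight-based contrast volume are used (6.6), and thickness is averaged over three sites in well-distended ileum (9.13). This makes drift smaller, not zero. The planned within-group correlation of shedding with imaging adds some supporting evidence, but it is not randomised either.

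Third, a reader might add regression to the mean, because recently ill infants are screened out. The documents do not support this: no infant is selected on ileal thickness, and no link between recent illness and thickness in these infants is given.

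Fourth, the within-arm change is the only information on an effect common to all arms, and a 95% interval carries the same information as the paired test. That also stands. Dropping the paired tests would be a matter of preference.

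**Conclusion.** The point holds as one of attribution. A within-arm change in terminal ileum thickness is an uncontrolled change over about five days. The randomised comparisons support statements about RV1 against RV5 and about adding routine vaccines, and the design cannot estimate rotavirus vaccine against none.

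On the stated assumptions, a drift of 0.2 to 0.4 SD raises the chance of a significant paired test from 5% to between 22% and 66% per arm with 37 pairs, or between 17% and 50% with 26. For at least one of four arms, the 19% without drift rises to between 63% and 99%, or between 51% and 94%. These figures show sensitivity to drift; they do not predict it. No document gives a drift, and at 0.1 SD the per-arm figure is only 8% to 9%.

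A reader might go further and conclude that the between-arm analysis is invalid, or that the trial needs a further arm. Neither follows: the change-score contrasts are valid for what they estimate, and stating the limits needs no new arm.

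**What to change.** In sections 3.3 and 10.3, state that only the between-arm change-score contrasts are randomised estimates of effect, and name what they estimate: RV1 against RV5, and with against without routine vaccines. State that the design cannot estimate rotavirus vaccine against none and cannot, by its randomised contrasts, detect an effect common to all arms.

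Report the four within-arm changes as means with 95% intervals, labelled as uncontrolled change over the study interval. The paired t-tests may stay as supportive. Add that these changes are not to be attributed to vaccination, nor passed to the planning of later studies under the Power paragraph as vaccine effect sizes. Use the same labels for the other imaging and cytokine outcomes that follow this analysis.

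The cost is wording only, with no added infants, visits or procedures. The downside is giving up an attribution that the design cannot support.

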## **4 Research Plan**

### **4.1 Overview of Study**

This study is a prospective clinical study designed to 1) examine the effects of RV1 and RV5 alone or with other routine immunizations on gastrointestinal anatomy 2) to assess the feasibility of conducting a larger scale study. Exploratory objectives include 1) to examine the effects of RV1 and RV5 with or without other routine immunizations on gastrointestinal motility 2) to examine the effects of RV1 and RV5 with or without other routine immunizations on blood and stool cytokines and inflammatory responses, including clinical reactogenicity events 3) to assess patterns and level of vaccine virus shedding after RV1 and RV5 4) to provide preliminary data assessing associations with the pattern of rotavirus vaccine strain (RV1 and RV5) shedding in the stool and blood, stool cytokine responses, and the anatomy and/or functional motility of the small intestine; and examine other factors such as maternal antibody, breast milk antibody, and human blood group antigens to see if these factors modify these responses and 5) to compare MRI and ultrasound imaging.

Healthy infants 6-13 weeks of age will be randomized (1:1:1:1) to receive either, RV1 alone, RV5 alone, RV1 with ACIP routinely recommended immunizations (Diphtheria, Tetanus and Pertussis (DTaP), *Haemophilus influenzae* type b (Hib), pneumococcal conjugate (PCV13), Hepatitis B (HBV) and

inactivated polio (IPV)) or RV5 with routine immunizations. Imaging study personnel and parents will be blinded to the rotavirus vaccine type; parents will be informed about the rotavirus vaccine type at the completion of the study. Up to 150 infants will be enrolled (see inclusion/exclusion below). The age-group of infants 6-13 weeks of age was chosen so enrolled infants can receive their first dose of rotavirus vaccine at the AAP/ACIP recommended age of 2 months (minimum age of 6 weeks and maximum age of 14 weeks and 6 days) and, to assure that other ACIP recommended vaccines can be administered at the recommended age.

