## **10 RANDOMIZATION, DATA MANAGEMENT, STATISTICAL PLAN**

### **10.1 Randomization Plan**

Upon meeting the inclusion and exclusion criteria, subjects will be randomized to one of the four vaccine groups: 1) RV1 alone, 2) RV5 alone, 3) RV1 with routine immunizations (DTaP, Hib, PCV13, HBV and IPV) or 4) RV5 with routine immunizations. This will be a simple randomization using SAS® PROC PLAN, which uses a random number generator to make assignments. Study statisticians will generate the assignments in advance of any enrollment. After obtaining informed consent, an unblinded research personnel will contact the statistician to obtain a specific subject's assignment. Parents and all study radiologists will be blinded as to which arm the child is randomized to until completion of the study. Parents will learn which rotavirus the child received at the completion of Visit 3. Parents will be informed about the specific other vaccines used in the study. If there is an urgent medical need to unblind during the study, then this can be done by calling the on call study staff.

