### **Power**

Since sample-sizes were predetermined and since this is a pilot study, no power calculations were conducted. Effect sizes will be reported from the results, to aid in the development of future studies.

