**APPENDIX 2. FEASIBILITY BENCHMARKS**

Item	Goal
Willingness to enroll	10% of subjects who are screened and found eligible will enroll in the study
Reason for non-enrollment	90% of those not enrolled will be asked for reason for refusal
Temperature monitoring	At least 70% of parents will check and record their baby's axillary temperature on at least 70% of the study days
Reactogenicity	At least 70% of the parents will complete the reactogenicity assessment for 70% of the days
Study visits	At least 70% of subjects will complete all study visits on time (per protocol) and remain in the study until completion
Blood draws	At least 70% of the blood draws will be successfully completed per protocol
MRI imaging	At least 70% of subjects will successfully complete both MRIs
Stool collection	At least 70% of parents will collect 70% of the 14 stool samples
Breast milk collection	At least 50% of breastfeeding moms will collect a breast milk sample
Saliva collection	At least 70% of subjects will successfully have saliva obtained
Receipt of 2 month vaccinations	90% of infants will receive remaining immunizations within ACIP guidelines
Remaining rotavirus doses	75% of infants will receive the second RV immunization with the same RV vaccine given as the first dose

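### The primary between-group model leaves out baseline ileum thickness and adds covariates only if they look imbalanced, so it can lose precision and is not fixed in advance

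*Combined protocol and SAP*

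**What the plan says.** Section 10.3 b) defines the endpoint: "The primary anatomical outcome will be the terminal ileum thickness measured in mm". It fits a general linear model with the four-level group as the only term, separately to the pre value, the post value and the change, and makes the change the primary one: "the primary between group comparisons is based on the pre-post change score". If the F-test supports it, six pairwise two-sample t-tests follow.

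Other covariates are handled by a screen. Socio-demographic and unspecified other variables are compared across groups, and then: "If some covariates are differentially distributed among the groups, those covariates will be controlled for in the primary analysis described above". No list of candidates and no criterion for a difference is given. Section 10.1 describes the allocation: "This will be a simple randomization using SAS". It names no stratification factors.

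The approach carries over to other outcomes, including "For the cytokines outcome (IL2, IL6, IL7, IL8, IL15, TNF) similar analysis described for the primary imaging outcome". The Power section makes no power calculation and says: "Effect sizes will be reported from the results, to aid in the development of future studies".

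**The concern.** There are two linked weaknesses.

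- **Baseline enters only by subtraction.** A change score is a baseline-adjusted analysis with the slope fixed at 1. The slope that minimises variance is rho × SD_post/SD_pre, where rho is the pre/post correlation. Unless that product equals 1, the group differences are estimated less precisely than the same data allow. Section 9.13 leaves inter-reader reliability to be determined, so the plan offers no ground for assuming a slope near 1.
- **The covariate set depends on the data.** Under simple randomisation, differences between groups at baseline arise by chance. A rule that reacts to them selects on observed imbalance and not on how well a covariate predicts the outcome. The model behind the reported primary estimate cannot be stated beforehand.

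The estimates are a main product of this pilot, because they are meant to inform later studies, and few infants may have two usable scans.

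**Working it through.** The plan has no power or precision figure to reproduce, so the two analyses are compared directly.

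**Inputs from the documents**
- Section 4.1: "Up to 150 infants will be enrolled", allocated 1:1:1:1.
- Appendix 2: "At least 70% of subjects will successfully complete both MRIs". Taken as a low case, 0.70 × 150 = 105 infants, or 105/4 ≈ 26 per arm.

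**Assumptions (not in the documents):** rho from 0.3 to 0.9, and k = SD_post/SD_pre of 0.8, 1.0 or 1.2.

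**Formulas**, with SD_pre = 1:
- Var(change) = 1 + k² − 2·rho·k
- Var(baseline-adjusted) = k²(1 − rho²)
- At k = 1 the ratio of the second to the first is (1 + rho)/2.

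Example at k = 1.2, rho = 0.5: 1.44 × 0.75 = 1.08, against 1 + 1.44 − 1.20 = 1.24, so the ratio is 0.87.

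**Ratio of adjusted to change-score variance (large sample)**

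| k | rho 0.3 | rho 0.5 | rho 0.7 | rho 0.9 |
|---|---|---|---|---|
| 0.8 | 0.50 | 0.57 | 0.63 | 0.61 |
| 1.0 | 0.65 | 0.75 | 0.85 | 0.95 |
| 1.2 | 0.76 | 0.87 | 0.97 | 0.98 |

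**Equivalent sample size at k = 1:** 105/0.65, 105/0.75, 105/0.85 and 105/0.95 give about 162, 140, 124 and 111. That is how many infants a change-score analysis needs to match the adjusted analysis of 105.

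**Where there is no gain:** rho × k = 1, for example rho = 0.7 with k = 1.43. Estimating one slope then costs a factor of about 1 + 1/(N − 6): 1.010 at N = 105 and 1.007 at N = 150.

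**Simulation of the variance ratio** (N = 105, simple randomisation to four arms, 6,000 runs): at k = 1 the ratios for rho 0.3, 0.5, 0.7 and 0.9 were 0.66, 0.74, 0.87 and 0.95, in line with the formula.

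**Chance that the screen flags something.** With m independent covariates tested at an assumed 5% level, the probability of at least one flag under sound randomisation is 1 − 0.95^m: 23% for m = 5, 34% for 8 and 40% for 10.

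**Simulation of the F-test** (1,500 runs per setting, equal arms, 5% level, 0.6 SD shift in one arm, k = 1). There were eight candidate covariates, one of which affected the outcome with coefficient 0.5. Power at N = 105:

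| Model | rho 0.3 | rho 0.5 | rho 0.7 |
|---|---|---|---|
| Change on group | 38% | 46% | 65% |
| Change on group + flagged covariates | 37% | 46% | 65% |
| Change on group + baseline | 49% | 57% | 70% |

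With no effect, rejection rates stayed at about 4 to 6% for all three models.

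**The case against.** The strongest reply is that the change score is a valid choice. It is unbiased under randomisation, keeps the within-group and between-group results on one scale, and suits a pilot with no power calculation. The plan also fits separate models to the pre and post values. If the same infants contribute to all three models, a reader could recover rho from the three residual variances and then work out the adjusted difference. Baseline thickness might also count among the unspecified other covariates. The size of the loss rests on assumed values: at k = 1.2 with rho of 0.7 or more it is only 2 to 3% of variance. The 70% figure is a feasibility floor, and withdrawn infants may be replaced (section 4.4). The screen shows no numerical harm in the simulation.

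Much of this stands and limits the importance of the point. The baseline part concerns efficiency, and the screening part concerns transparency. Three parts do not stand:
- An adjusted estimate that a reader could reconstruct is not one that the plan tests or reports.
- If baseline entered through the screen, it would still enter only when it looked imbalanced, so the model would still depend on the data.
- The variance ratios do not depend on N, so they hold at 150 as well.

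**Conclusion.** The concern holds, as an improvement worth making and not as an error that invalidates the analysis. With equal visit SDs, adjusting for baseline removes 35% of the variance of the between-group difference at rho = 0.3, falling to 5% at rho = 0.9. Across all the assumed SD ratios, the saving runs from 2% to 50%. It is nil where rho × SD_post/SD_pre is exactly 1, and there the cost is about 1% at 105 infants. The wording and the algebra are certain. The practical size is not, because the documents give neither the correlation nor the SDs. Separately, the covariate rule leaves the primary model undetermined until the data are seen, and in the simulation it brought no gain in power.

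**What to change.** - State the primary between-group model as Visit 2 (Day 5) terminal ileum thickness on group and baseline thickness. Using change as the response gives the same group contrasts.
- Take the six pairwise comparisons as contrasts from this model, in place of the two-sample t-tests, so that they are adjusted too.
- Name any further covariates in advance, on prognostic grounds. Delete the rule based on observed differences, and present baseline characteristics descriptively.
- Keep the unadjusted change score as a sensitivity analysis, and leave the within-group paired t-tests unchanged.
- Use the same form for the other continuous imaging and cytokine outcomes. Say how baseline is handled if the rank-based fallback is used, since the linear model does not apply there.

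The cost is a change of wording. Baseline thickness exists for every infant with a usable change score, so no data are lost. One residual degree of freedom is spent: 146 to 145 with 150 evaluable infants, or 101 to 100 with 105. The normality check and the optional pooling of arms also depend on the data, and this change does not settle them.
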